8.4.2. Population Pharmacokinetics Analysis

On Day 3, the plasma samples will be collected before the morning dose (at the trough). These data will allow for analysis of relationships between trough plasma concentrations and clinical and virologic response.

Day 3 trough plasma concentrations of tizoxanide and tizoxanide glucuronide will be summarized descriptively for each of the treatment groups. Exploratory analyses will be conducted to evaluate the relationships between plasma concentrations and age, race, gender, body weight, body mass index, concomitant medications, changes in viral titer over time, time from first dose to Symptom Response and adverse events.

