5.2. Baseline (day 1, same day as screening evaluation)

At baseline, the following procedures will be carried out:

1. Collection of two nasopharyngeal swabs (one from each nostril) using nylon flocked dry swabs (Copan Diagnostics) for RT-PCR and culture.
2. Collection of blood sample for laboratory safety tests.
3. Collection of a urine sample for routine urinalysis (glucose, protein and blood).
4. Review and recording of any concomitant medications.
5. Provision of an electronic diary to subject via his/her own smartphone or a provisioned device, and subject completion of baseline electronic diary under supervision and instruction of study site personnel, including the Practice Diary, FLU-PRO Questionnaire, Activity Diary, and Study Drug Intake and Temperature Diary.
6. Randomization and dispensing of study medication (medication assigned in sequential order).

7. Administration of the first dose of study medication with food (< 1 hour after food intake) under observation of Investigator or a member of Investigator's staff, and entry in Study Drug Intake and Temperature Diary.
8. Instruct subject regarding:
 - a. *Administration of study medication.* Subjects will be instructed to take the study medication (two tablets) twice daily with food (< 1 hour after food intake, preferably a high-fat meal but at a minimum a cereal bar). The subject should take his/her second dose as close as possible to 12 hours after the first dose. Then he/she will take the study medication every 12 hours for the remaining 4 days.
 - b. *Completion of subject diary.* Subjects will be instructed on completion of the electronic diary.
 - c. *Use of birth control.* Female subjects of childbearing potential, if sexually active, will be instructed to continue an acceptable method of birth control for the duration of the study and for 1 month post-treatment. Acceptable methods of birth control include a double barrier method, oral birth control pills, an IUD, or medroxyprogesterone acetate administered intramuscularly.
 - d. *Follow-up visits:* Subjects will be instructed to return to the clinic for follow-up on Day 7 and Day 22.
 - e. *Seeking emergency care or contacting the study physician or nurse:* Subjects must be informed to seek emergency medical care or contact the study physician or nurse if they develop any of the following symptoms listed below during the full 22-day study and follow-up period.

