5.5. Day 2 and 3 Evaluations

A study physician, nurse or other study personnel will visit each subject at home (or at the clinic or another location as agreed with the subject) on each of Days 2 and 3 to (i) collect two nasopharyngeal swabs for detecting and quantifying EV/RV, and (ii) screen for potential complications and adverse events. Subjects will be referred for immediate care as needed based on the screening. All information gained from these visits will be included in the case report forms for each subject. In addition, a blood sample for pharmacokinetics will be collected on Day 3. The Day 2 and Day 3 visits will occur at approximately the same time of day that the patient took his/her first dose of study medication (approximately 24 and 48 hours after the first dose). On Day 3, the blood sample for pharmacokinetics will be collected before the first dose of that day.

Study sites or subjects may opt out of these Day 2 and Day 3 visits due to site staffing, subject availability or other practical considerations or preferences; nevertheless at least 75% of subjects enrolled in the trial are expected to complete the Day 2 and Day 3 visits and related procedures (for viral kinetics and pharmacokinetics).

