8. STATISTICAL CONSIDERATIONS

8.1. Sample Size Calculations

The Symptom Response definitions for this study will be derived from the subjects' FLU-PRO questionnaire responses as described in section 8.3 below. The FLU-PRO-derived endpoint is expected to track very closely to return to usual health status (a daily yes/no question in the FLU-PRO questionnaire), which in turn is expected to track very closely to ability to perform 100% of normal activities. We assume, therefore, that the cumulative distributions of time to Symptom Response for the placebo treatment group will closely reflect historical data from Romark Study RM08-3002 for time from first dose until the EV/RV-infected subjects report that they are able to perform 100% of usual activities (see placebo curve in chart below). Then, to calculate sample size, we assume that treatment with NTZ treatment should result in reduction of at least 48 hours in median time to symptom response. The following curves have been developed for determining sample size.

Based upon these curves, a sample size of 530 subjects with laboratory-confirmed EV/RV infection (i.e. 265 for each of the 2 groups) will provide 90% power to detect a statistically significant difference in the survival distributions between the NTZ and placebo groups (2-sided alpha of 0.05). This calculation was performed for the Gehan rank test using SAS PROC POWER (SAS 9.4) with the curves shown above (proportion not recovering by the end of each day was used as input) and censoring at day 21 (hour 504). Assuming that up to 12% of subjects will have incomplete data, we arrive at a sample size of 600 subjects in total, 300 per treatment group to yield at least approximately 530 with complete data (all 600 subjects will be included in the primary analysis with subjects with incomplete data censored as of their last entry).

Based upon these calculations, the study will enroll at least 600 subjects with laboratory-confirmed EV/RV infection up to a maximum of 700 subjects with laboratory-confirmed EV/RV infection. We estimate that this will require enrollment of up to 1,750 subjects in total assuming an EV/RV-positive rate of at least 40%.

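### The Day 3 PK sample is labelled a pre-morning-dose trough although its visit can fall in the afternoon, and SAP 11.6.1 analyses all values without hours since last dose or a sampling window

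*Protocol*

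**What the plan says.** **Sampling rule.** Protocol 8.4.2: "On Day 3, the plasma samples will be collected before the morning dose (at the trough". It gives the purpose as: "These data will allow for analysis of relationships between trough plasma concentrations and clinical and virologic response".

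**Visit time.** Protocol 5.5: "Day 3 visits will occur at approximately the same time of day that the patient took his/her first dose", which it glosses as "approximately 24 and 48 hours after the first dose". It then says: "On Day 3, the blood sample for pharmacokinetics will be collected before the first dose of that day". SAP 8.2 also ties the sample to the first Day 3 dose. The first dose is taken in the clinic on the enrolment day, and neither document restricts its clock time.

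**Dosing.** Protocol 5.2 puts the second dose as near as possible to 12 h after the first, and continues: "Then he/she will take the study medication every 12 hours for the remaining 4 days". SAP 8.2 repeats the 12 h rule for the second dose but describes dosing as morning and evening.

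**Analysis.** For the PK exposure, SAP Table 14 lists only the Day 3 tizoxanide and glucuronide values. SAP 11.6.1 relates them to demographics, viral titer change, Time to Symptom Response and adverse events by Spearman, Pearson or Kruskal-Wallis methods. Time since last dose is not a factor, and no sampling window is set. The PK listing in SAP Table 16 shows the visit and its date but no draw time. Dose intake times are recorded in the electronic diary (Protocol 5.10).

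**The concern.** The two documents describe one sample in three ways: before the morning dose, before the first dose of Day 3, and at the clock time of the first clinic dose. For a subject first dosed in the morning these coincide. For a subject first dosed at 15:00 they need not.

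Strict 12-hourly dosing from 15:00 means doses at 15:00 and 03:00. Some subjects may well drift to ordinary morning and evening times, which is how SAP 8.2 describes the regimen. The interval before the Day 3 draw is then no longer fixed at 12 h.

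Relating pharmacokinetics to clinical or virologic response is a stated objective in both documents, and the Day 3 sample is its only exposure measure. If intervals vary and are not recorded in the analysis, a weak exposure-response relationship cannot be told apart from timing noise.

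**Working it through.** The plan states no figure on this point, so there is none to reproduce. The check has two parts.

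**1. Do the sampling rules conflict?** Under Protocol 5.2 doses fall at hours 0, 12, 24, 36 and 48. A pre-dose draw at hour 48 is 48 − 36 = 12 h after the last dose, whatever the clock time. Protocol 8.1 uses "censoring at day 21 (hour 504" in the sample size calculation, and 504/24 = 21, so on that convention Day 3 begins at hour 48. The first dose of Day 3 is then the one due at the visit, and Protocol 5.5 is consistent with itself. Only 'morning' in Protocol 8.4.2 fails for an afternoon start.

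Now assume that a subject first dosed at 15:00 moves to 08:00 and 20:00. A pre-dose draw at 15:00 on Day 3 would be 19 h after the last dose. A visit moved to 08:00 would restore 12 h.

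**2. How much does timing matter?**

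Inputs:
- Day 7 half-life (Protocol Table 1, 12 healthy volunteers): tizoxanide 2.19 h, glucuronide 4.99 h.
- Day 3 trough CV (Protocol Table 2): 101% and 72.8%.
- Assumptions: mono-exponential decline, one common rate, and timing error unrelated to a subject's usual exposure.

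Concentration relative to the 12 h value is 2^(−(t − 12)/half-life):

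| Hours since last dose | Tizoxanide | Glucuronide |
|---|---|---|
| 10 | 1.88 | 1.32 |
| 12 | 1.00 | 1.00 |
| 14 | 0.53 | 0.76 |
| 16 | 0.28 | 0.57 |
| 20 | 0.08 | 0.33 |

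With the tabulated glucuronide rate constant (0.201/h), the 16 h and 20 h glucuronide values are 0.45 and 0.20.

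For the correlations, tizoxanide k = ln 2/2.19 = 0.3165/h and the between-subject log variance is v = ln(1 + 1.01²) = 0.703. A log-scale correlation is multiplied by √(v/(v + k² × variance of hours since last dose)). For an assumed SD of 1, 2, 3 or 4 h the factor is 0.94, 0.80, 0.66 or 0.55.

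A second scenario assumes that a share p of samples is drawn 4 to 8 h late (uniform) and the rest on time. The variance is 37.333p − (6p)². The mean trough factor is 1 − p × [1 − (e^(−4k) − e^(−8k))/(4k)]. The Spearman and Pearson columns come from simulation (2,000,000 draws, assumed true log-scale correlation 0.3). All entries are for tizoxanide.

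| p | Variance (h²) | Log-scale factor | Spearman | Pearson, raw values | Mean trough |
|---|---|---|---|---|---|
| 0% | 0 | 1.00 | 1.00 | 1.00 | 1.00 |
| 1% | 0.370 | 0.97 | 0.99 | 0.99 | 0.99 |
| 10% | 3.373 | 0.82 | 0.87 | 0.93 | 0.92 |
| 25% | 7.083 | 0.71 | 0.73 | 0.84 | 0.79 |
| 50% | 9.667 | 0.65 | 0.63 | 0.70 | 0.58 |

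The glucuronide, with v = ln(1 + 0.728²) = 0.425 and k = ln 2/4.99 = 0.1389/h, is less sensitive: log-scale factors 0.99, 0.93, 0.87 and 0.83 for p from 1% to 50%. What attenuates a correlation is the spread of intervals, not lateness itself. If every sample were 4 to 8 h late, the tizoxanide log-scale factor would be 0.92.

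**The case against.** The strongest reply is that the protocol's own regimen delivers the trough: followed as written, it makes the hour-48 pre-dose draw a 12 h sample for everyone. Morning and evening appears in a study-description paragraph of the SAP, which does not instruct subjects. This stands, and it limits the protocol defect to one word plus an ambiguity.

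A reader might go further and infer that an afternoon visit cannot yield a valid trough unless a dose is held, or that the planned correlations are biased by a known amount. The documents support neither. No section tells subjects to hold a dose. Protocol 5.5 says only approximately the same time of day, and allows visits at home or another agreed place. The share of off-time samples, the clock schedule and the delays used above are all assumed.

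The decay rate is also extrapolated. It comes from profiles to 12 h after a morning dose, while a late sample would follow an evening dose. Mean pre-morning-dose tizoxanide was 3.24, 3.80 and 3.26 µg/mL on Days 4 to 6 (Protocol Table 2), against 1.72 µg/mL at the end of the Day 7 profile (Table 1), so overnight kinetics may differ. With an assumed half-life of 3.5 h, the values at 16 and 20 h become 2^(−4/3.5) = 45% and 2^(−8/3.5) = 21%. That is smaller, but still a two- to five-fold change.

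Finally, draw time may already be collected. The case report form is not among the documents, and Protocol 5.5 says: "All information gained from these visits will be included in the case report forms for each subject". But a recorded time does not help unless the analysis uses it, and SAP 11.6.1 does not.

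**Conclusion.** The point holds as a low-cost improvement. The word 'morning' in Protocol 8.4.2 does not fit the visit timing in Protocol 5.5. SAP 11.6.1 treats all Day 3 concentrations as comparable without checking when they were drawn. For a drug with a half-life near 2 h, a few hours' difference changes the concentration several-fold.

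The size in this trial is unknown. It runs from no effect, if all samples are about 12 h post-dose, to a tizoxanide Spearman correlation multiplied by about 0.63 in the most extreme share considered (half of samples 4 to 8 h late). Those factors rest on the assumed schedule and delays, a common rate of decline, and timing error independent of usual exposure.

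Only the exploratory PK analysis in NTZ-treated infected subjects is affected, and its samples come from visits that sites or subjects may decline. The primary and secondary tests, their alpha and the sample size are not touched.

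**What to change.** - **Protocol 5.5 and 8.4.2, SAP 8.2:** define the sample as drawn just before the dose due at about 48 h, about 12 h after the last dose. Drop the references to the morning dose and to the first dose of the day.
- **Data:** confirm that draw time is captured, or add the field. Derive hours since last dose from the diary intake times and list it beside each concentration in SAP Table 16.
- **SAP 11.6.1 and Table 14:** add hours since last dose as a variable. Adjust the exposure-response analyses for it, by partial correlation or by regression on log concentration. Limit the trough summary to a prespecified window around 12 h, for example 10 to 14 h; the sponsor should set the limits.

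The dosing regimen does not change. The cost is wording in two protocol sections and two SAP sections with their tables, one derived variable, possibly one new data field, and the loss of some samples from the trough summary. Adjustment removes the timing error fully only if one rate of decline fits all subjects, so it reduces the problem rather than guaranteeing its removal.

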8.4.3. Safety Analyses

All randomized subjects who receive the study medication will be evaluated for drug safety. Safety analyses will be done descriptively.

9. INVESTIGATIONAL PRODUCTS

9.1. Drug Regimens, Administration and Duration

Group 1 (NTZ): Subjects will receive two NTZ 300 mg tablets b.i.d. with food (< 1 hour after food intake) for 5 days.

Group 2 (Placebo): Subjects will receive two placebo tablets b.i.d. with food (< 1 hour after food intake) for 5 days.

The food prior to drug intake should preferably be a high-fat meal, but at minimum a cereal bar.

9.2. Identity of Investigational Products

NTZ 300 mg and placebo tablets were manufactured for Romark Laboratories, L.C. by [REDACTED] in the United States. The active formulation for this study is a yellow, film-coated tablet that contains 300 mg NTZ plus standard excipients. The placebo tablet will have the same appearance and inactive ingredients as the active tablet.

9.3. Packaging and Labeling

NTZ or placebo tablets will be packaged for each subject in a white HDPE bottle, each containing 20 tablets. The subjects will take two tablets at each dosing time point. The bottles will be stored at room temperature and will bear a label with the following information:

Table 11: Study Medication Label

20 Tablets	Study N° RM08-3005	Treatment N°: XXXX		
Lot:	Principal Investigator:			
Take 2 Tablets by Mouth with Food Twice Daily				
Caution: New Drug-Limited by Federal Law to Investigational Use				
STORE AT ROOM TEMPERATURE • DO NOT USE BEYOND END OF STUDY				
KEEP OUT OF REACH OF CHILDREN				
Study Sponsor: The Romark Institute for Medical Research				

9.4. Drug Accountability

Medication will be dispensed at baseline. Medication compliance will be reviewed with each subject during the Day 2-5 Telephone Monitoring. At the Day 7 visit, subjects will be asked to return the bottle in which the medication was dispensed along with any unused medication.

The Investigator or designee is required to maintain adequate records of the disposition of all study drug, including dates, quantity and use by subject. Unused supplies must be returned to the Sponsor.

9.5. Subject Compliance

Subject compliance with the protocol will be checked by the Investigator and recorded in the EDC system at each visit.

Subjects will be considered non-compliant (major protocol violation) if they have missed more than two doses of the study medication during the first three days of the study. Non-compliance will not be cause for discontinuation of subject participation in the study.

9.6. Disallowed Medication

The following medications will not be allowed during the study: topical or systemic decongestants, nasal corticosteroids, and any prescription or non-prescription medications classified as (i) expectorants and cough preparations, (ii) analgesics and antipyretics or (iii) antihistamines (American Hospital Formulary Service (AHFS) classification). As an exception to this rule, subjects will be allowed to use acetaminophen and/or dextromethorphan as necessary for disabling symptoms .

Medications for pre-existing conditions that are not excluded (see exclusion criteria) should be continued as prescribed. The use of such medication will be recorded in the EDC system.

10. ADVERSE EVENTS

The term “adverse event” is defined for purposes of this study as any unwanted physical, psychological or behavioral change experienced by a subject during the course of the study and after taking the first dose of study medication regardless of its severity or relation to the study. Adverse events may include symptoms, signs, unexpected worsening of pre-existing conditions, clinically significant changes in laboratory values, diseases and syndromes, and significant and unexpected failures of pharmacological action of other medications. Symptoms of colds due to EV/RV infection (cough, sore throat, nasal obstruction, fatigue, headache, myalgia, feverishness) and complications of colds will not be reported as adverse events.

Adverse events will be recorded on the appropriate EDC forms throughout the study, and the severity of each adverse event will be graded on a four-point scale: mild, moderate, severe, or life-threatening ([See Appendix II](#)). The duration of the adverse event and relationship to the study drug will also be recorded. All adverse events must be followed until their resolution or stabilization even beyond the planned study period.

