1.2.6. Overview of Other Experience in Clinical Trials and Post-marketing Surveillance

NTZ has been marketed for diarrheal disease caused by *Giardia* or *Cryptosporidium* in the United States since 2003 and in Latin America since 1996. It is estimated that more

than 250 million patients have been exposed to NTZ worldwide. No drug-related serious adverse events have been reported during post-marketing experience with NTZ.

Phase 2 and 3 clinical studies have been conducted in approximately 5,600 subjects to evaluate the safety and efficacy of NTZ in treating parasitic, bacterial and viral infections. During these studies, no drug-related serious adverse events have been observed. The side effects have been usually of a mild transient nature, and less than 1% of subjects have discontinued therapy because of an adverse event. The most common adverse events reported in clinical trials include abdominal pain, chromaturia, diarrhea, dizziness, headache, nausea and vomiting and did not differ significantly from those of placebo except for chromaturia which was reported by 4 to 5% of subjects and is attributed to urinary excretion of NTZ metabolites. Clinical chemistry and hematology obtained before and after treatment have not revealed any abnormalities attributable to the test drug ([Clinicaltrials.gov](https://clinicaltrials.gov) 2018b).

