10.2. Clinical Adverse Events

At the time of each return visit, the subject will be questioned regarding the occurrence and nature of any adverse events. All events must be recorded in the subjects' medical records and in the EDC system. Any subject affected will be examined by the Investigator as deemed necessary to ascertain the course of the event and any residual effects.

All moderate and severe adverse events will be reviewed by the Principal Investigator who will determine using his/her best clinical judgment whether they warrant the subject to be discontinued from the study. The Sponsor will be notified immediately if a subject is discontinued from the study. For all adverse events that require the subject to be discontinued from the study, relevant clinical assessments and laboratory tests will be repeated as clinically indicated until final resolution or stabilization of the event(s).

All subjects will be instructed to contact the Investigator, Investigator's assistants, or clinical personnel should the subject have any serious adverse experiences. Serious adverse events (SAEs), including death regardless of the cause, must be reported to the Sponsor immediately (within 24 hours of the initial report).

A serious event requiring immediate notification by telephone is an event that:

- results in death
- is life threatening
- requires inpatient hospitalization or prolongation of an existing hospitalization
- is a persistent or significant disability/incapacity
- is a congenital anomaly/birth defect
- an important medical event that may not result in death, be life-threatening, or require hospitalization but, based upon appropriate medical judgment, may jeopardize the subject and may require medical or surgical intervention to prevent one of the outcomes listed above.

An overdose is defined as any intentional or unintentional consumption of the drug by any route that exceeds the highest dose stated in the Investigator's Brochure or in an investigational protocol, whichever dose is larger. Overdoses without an associated adverse event should be recorded, but not reported as an adverse event.

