21.2. Appendix II: Toxicity Grading for Adverse Events

[Derived and adapted from “Guidance for Industry: Toxicity Grading Scale for Healthy Adult and Adolescent Volunteers Enrolled in Preventive Vaccine Clinical Trials”, US Dept. of HHS, FDA, CDER, September 2007]

Table 14: Table for Clinical Abnormalities: Vital Signs

Vital Signs*	Mild (Grade 1)	Moderate (Grade 2)	Severe (Grade 3)	Potentially Life Threatening (Grade 4)
Fever (°C)** (°F)**	38.0 – 38.4 100.4 – 101.1	38.5 – 38.9 101.2 – 102.0	39.0 – 40 102.1 – 104	> 40 > 104
Tachycardia – beats per minute	101 – 115	116 – 130	> 130	ER visit or hospitalization for arrhythmia
Bradycardia – beats per minute***	50 – 54	45 – 49	< 45	ER visit or hospitalization for arrhythmia
Hypertension (systolic) – mm Hg	141 – 150	151 – 155	> 155	ER visit or hospitalization for malignant hypertension
Hypertension (diastolic) – mm Hg	91 – 95	96 – 100	> 100	ER visit or hospitalization for malignant hypertension
Hypotension (systolic) – mm Hg	85 – 89	80 – 84	< 80	ER visit or hospitalization for hypotensive shock
Respiratory Rate – breaths per minute	17 – 20	21 – 25	> 25	Intubation

* Subject should be at rest for all vital sign measurements.

** Oral temperature; no recent hot or cold beverages or smoking.

*** When resting heart rate is between 60 – 100 beats per minute. Use clinical judgment when characterizing bradycardia among some healthy subject populations, for example, conditioned athletes.

Table 15: Table for Clinical Abnormalities: Systemic (General)

Systemic (General)	Mild (Grade 1)	Moderate (Grade 2)	Severe (Grade 3)	Potentially Life Threatening (Grade 4)
Nausea/vomiting	No interference with activity or 1-2 episodes/24 hours	Some interference with activity or > 2 episodes/24 hours	Prevents daily activity, requires outpatient IV hydration	ER visit or hospitalization for hypotensive shock
Diarrhea	2-3 loose stools or <400 gms/24 hours	4-5 stools or 400-800 gms/24 hours	6 or more watery stools or >800 gms/24 hours or requires outpatient IV hydration	ER visit or hospitalization
Headache	No interference with activity	Repeated use of non-narcotic pain reliever >24 hours or some interference with activity	Significant; any use of narcotic pain reliever or prevents daily activity	ER visit or hospitalization
Fatigue	No interference with activity	Some interference with activity	Significant; prevents daily activity	ER visit or hospitalization

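### Protocol section 10 bars cold symptoms and complications from adverse event reporting without an attribution, relatedness or seriousness test, in conflict with 10.1–10.3, Appendix II and SAP Table 8

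*Protocol*

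**What the plan says.** Protocol section 10 opens with a broad definition: an adverse event is any unwanted change "after taking the first dose of study medication regardless of its severity or relation to the study". Its examples include "unexpected worsening of pre-existing conditions". The same paragraph then removes a group of events from adverse event reporting: "Symptoms of colds due to EV/RV infection (cough, sore throat, nasal obstruction, fatigue, headache, myalgia, feverishness) and complications of colds will not be reported". No grade, cause, timing or seriousness condition is attached.

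Other places bear on the same events:

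- **Protocol 8.3** defines complications of colds. The list includes worsening of earlier health conditions, hospitalization and death.
- **Protocol 10.1 and 10.2** make an event serious if it is fatal or if it "requires inpatient hospitalization or prolongation of an existing hospitalization". SAEs go to the sponsor within 24 hours. **Protocol 10.3** adds immediate notice of fatal, life-threatening or unexpected experiences and of serious reactions, whatever the view on cause.
- **Appendix II Table 15** grades headache, fatigue and myalgia from 1 to 4. Grade 2 headache, for example, is "Repeated use of non-narcotic pain reliever >24 hours or some interference with activity".
- **Protocol 1.2.6**, on earlier NTZ experience, says "The most common adverse events reported in clinical trials include abdominal pain, chromaturia, diarrhea, dizziness, headache, nausea and vomiting", and adds that these "did not differ significantly from those of placebo except for chromaturia".
- **SAP Table 8** gives the source of the complications endpoint: adverse events that the investigator designates as complications.
- **Protocol 11.1** stops the study if more than 5% of subjects have a related Grade 3 or 4 adverse event. **SAP 12.1.1 and 12.1.2** build the safety tables from treatment-emergent adverse events and SAEs.

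**The concern.** The safety tables and the stopping rule count adverse events and nothing else. An event that section 10 declares not to be an adverse event cannot reach them. Two groups are exposed: serious complications, which other sections treat as SAEs, and listed symptoms that an investigator thinks the drug may have caused.

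The trial has no independent data monitoring committee (Protocol 14), so the adverse event listings that feed the 5% rule carry much of the safety oversight. Sites with the same patient in front of them could also act differently, depending on which section they follow.

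**Working it through.** **1. The passages side by side**

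| Event | Section 10 exclusion | Elsewhere |
|---|---|---|
| Unexpected worsening of an earlier condition | Not an adverse event, if it is a complication under 8.3 | An adverse event, by the definition in the same paragraph |
| Hospitalization or death from the cold or its complications | Not an adverse event | SAE with 24-hour reporting (10.1, 10.2) |
| Headache, fatigue, myalgia | Not adverse events | Graded 1–4 (Appendix II Table 15) |
| Any complication | Not an adverse event | An adverse event that the investigator flags (SAP Table 8) |

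**2. Three cases followed through the text**

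- *A subject is hospitalized because of the cold.* It is a complication under 8.3 and so not an adverse event under section 10. It is an SAE under 10.1, and Appendix II Table 16 puts hospitalization at Grade 4. Section 10.1 lets an event be possibly related even when another cause is present, so it could count towards the 5% rule. Under section 10 that judgement is never reached.
- *A headache starts on Day 4 and the investigator rates it probably related.* Read as a list, section 10 excludes it. Read as covering only symptoms of the cold, section 10 leaves it reportable. The text does not choose.
- *A site records a complication.* SAP Table 8 needs an adverse event to flag. A site that obeys section 10 has none.

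**3. Whether other outputs fill the gap**

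- Complications are compared by arm in the infected population (SAP 11.4.2) and in all treated subjects (SAP 11.5.8). Their listing (SAP Table 15) has no field for seriousness or relation to study drug, while the adverse event listing (SAP Table 16) has both. SAP Appendix 2 assigns the complications listing to the infected population only.
- The individual-symptom analysis (SAP 11.5.1) is exploratory and restricted to the infected population. It drops subjects whose symptom already meets response at the first record, so it cannot show a new symptom in them.
- The exclusion is worded for colds due to EV/RV. The plan's own figure reproduces: 700 / 0.40 = 1,750 subjects. That leaves 1,750 − 700 = 1,050 EV/RV-negative subjects, and the documents do not say how the exclusion applies to them.

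**4. Size**

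No rate for headache, fatigue or serious complications in this setting is given, so the real effect cannot be calculated. What follows from the rule is the count needed to exceed 5%, floor(0.05 × N) + 1: 31 subjects at N = 600, 36 at 700 and 88 at 1,750. If all 88 were on NTZ, that is 88 / 875 = 10.1% of the arm.

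An illustration with assumed rates: let q be the rate of other related Grade 3–4 events in all subjects, and h the further rate, on NTZ only, of subjects whose only such event falls under the exclusion. At one look with N = 1,750, the chance of crossing is P(X ≥ 88), with X binomial at rate q if excluded events are not counted and q + h/2 if they are.

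| q | Not counted | h = 0.5% | h = 1% | h = 2% | h = 3% |
|---|---|---|---|---|---|
| 1% | about 0 | about 0 | about 0 | about 0 | about 0 |
| 3% | about 0 | 0.01% | 0.06% | 1.9% | 15.7% |
| 4% | 1.9% | 6.3% | 15.7% | 49.3% | 82.0% |
| 4.5% | 15.7% | 30.7% | 49.3% | 82.0% | 96.4% |

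The exclusion matters to the stopping rule only if other related severe events already run close to 5%. The loss from the safety tables does not depend on that.

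**The case against.** Keeping symptoms of the disease out of the adverse event tables is a legitimate design choice, and the diary already measures them. Beyond that, four stronger readings that a reader might infer are not supported.

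- *That the protocol names headache as a drug effect.* It does not. Section 1.2.6 says only chromaturia differed significantly from placebo, and section 3 names only diarrhea as higher at this dose (8.1% against 5.8%).
- *That a headache can never be recorded.* The exclusion is attached to symptoms of EV/RV colds. A headache attributed to the drug, or starting after the cold has gone, can be read as falling under the general definition. What is missing is the rule that says so.
- *That serious events would go unreported to the sponsor.* Sections 10.2 and 10.3 keep a notification duty. They do not say that the event then enters the SAE tables or the 5% count.
- *That complications vanish from the data.* They are compared by arm in two populations and listed with term, severity and outcome. The missing items are their status as adverse events, and their seriousness and relatedness.

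Table 15 is also weaker evidence than it looks. Appendix II is an adapted general scale that grades calcium, magnesium and clotting tests, none of which is in the laboratory panel of section 5.11. A grading row alone does not prove that the term was meant to be collected.

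All of this stands, and it narrows the point. It does not resolve the conflicts over serious complications, worsening of earlier conditions and SAP Table 8.

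**Conclusion.** The rule is wrong as written, not merely short of detail. The clearest fault is in complications: section 10 says that they are not adverse events, while its own definition, 10.1–10.2 and SAP Table 8 treat some or all of them as such. For the listed symptoms the fault is the absence of an attribution and relatedness rule. Headache illustrates this as a commonly reported event in earlier NTZ trials that is not shown to differ from placebo.

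The consequence rests on sites following section 10 literally. In that case serious complications and drug-attributed listed symptoms are absent from the treatment-emergent and SAE tables and from the stopping count. How many events that is cannot be stated from the documents, and the crossing probabilities above rest wholly on assumed rates.

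**What to change.** Reconcile Protocol section 10 with 8.3, 10.1–10.3, Appendix II and SAP Table 8, and state two things.

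1. **Complications.** They are captured as adverse events that the investigator flags, as SAP Table 8 assumes. One that meets a seriousness criterion in 10.1 is reported under 10.2 and counted in the SAE tables, even if it also counts as an efficacy complication.
2. **Symptoms.** The exclusion covers only symptoms attributed to the presenting cold. A listed symptom is recorded as an adverse event if it is serious, if the investigator rates its relation to study drug as possible, probable or definite, or if it newly starts after the cold has resolved.

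Do not extend this to every Grade 3 or higher cold symptom whatever its cause. Grade 3 headache and fatigue in Table 15 include symptoms that stop daily activity, so ordinary illness would enter the tables. If NTZ shortens colds, those events would fall more on placebo and mix efficacy into safety.

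The cost is amendment wording, matching SAP text and site instruction. There will be somewhat more adverse event records, not necessarily equal between arms.
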